### 13.3 Determination of Sample Size

Sample size for this study is determined on grounds of feasibility and common practice in similar trials.

### 13.4 Sample Size Justification

No formal sample size calculation has been performed for this phase 2 trial, but the sample size is typical for phase 2 trials, and in our experience, has been useful to assess the immunogenicity of vaccines.

Results of the predecessor study MV-CHIK-101 allow to assess the usefulness of the chosen sample size:

In phase I study MV-CHIK-101, a GMT of 7.3 (LOG10 SD 0.254) at day 28 in the placebo group and a GMT 13.7 (LOG10 SD 0.515) in the lowest dose group (MV-CHIK 0.05 mL = 1.5 x10^4 TCID50) was observed. Both higher dose groups (MV-CHIK 0.25 mL = 7.5 x10^4 TCID50; 1 mL = 3 x10^5 TCID50) demonstrated higher GMTs of 48 (LOG10 SD 0.466) and 45.7 (LOG10 SD 0.579).

In the present phase II study, the sample size of 60 subjects in the MV-CHIK dose group vs. 10 subjects in the corresponding control group within each dose group A-D will allow for a detection of a GMT of 15.4 (MV-CHIK) vs. 7.3 (placebo) with a LOG10 SD of 0.6 vs. 0.26 and statistical power of 80% (two-sided alpha=5%, unequal-variance t-test). Between dose groups, the sample size of 60 subjects per group will allow for a comparison of a GMT of 45.7 vs. 22.4 (LOG10 SD 0.6 for both groups) with a statistical power of 80% (two-sided alpha=5%, equal-variance t-test).

Since the magnitude of GMTs and LG10 DS in this assessment is comparable to the observed results in study MV-CHIK-101, and the statistical methodology applied in the current study has a higher statistical power than pairwise t-tests, the chosen sample size seems adequate.

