### 13.1 Immunogenicity Analysis

The primary immunogenicity analysis will compare the anti-chikungunya PRNT50 antibody geometric mean titer (GMT) 28 days after one or two immunizations in the Per Protocol (PP) analysis population between the treatment groups. GMTs and GMT ratios will be estimated by applying an analysis of variance including the factor vaccination group. This will be done using log-10 transformed data and taking the anti-log of the resulting point estimates for the least squares means, least squares means differences and the corresponding 2-sided 95% CIs. P-values will also be provided to compare GMTs for the MV-CHIK groups (pairwise comparisons adjusted for multiple comparisons according to Tukey-Kramer; groups A vs. B, C vs. D, M1 vs. M2), e.g. 28 days after the 2nd MV-CHIK dose, etc. Likewise, SCRs will also be compared between groups. Seroconversion will be defined as anti-Chikungunya PRNT50 titers  $\geq 10$ .

Measles ELISA titers will be analyzed as described above. In addition, the effect of pre-existing anti-measles immunity will be assessed: The CHIKV PRNT50 titers 28 days after first vaccination, between the four baseline measles titer groups, defined by baseline percentiles

(25%, 25-50%, 50-75%, 75-100%), will be compared. No stratification by dose groups is intended.

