2.7 Inferential Analyses

Inferential analysis on immunogenicity endpoints will only be performed on the PP and ITT population. The significance level will be 0.05. All p-values will be two-sided and rounded to four decimal places.

GMTs and GMT ratios will be estimated by applying an analysis of variance (ANOVA) by using log-10 transformed data and taking the anti-log of the resulting point estimates for the least squares means, least squares means differences and the corresponding 2-sided 95% Cls. Pairwise comparisons for multiple comparisons will be adjusted according to Tukey-Kramer. For the definition of the baseline percentiles treatment groups A, B, C and D will be used.

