2.7.1 Inferential Analysis for the Primary Endpoint

The primary immunogenicity analysis will compare the PRNT₅₀ antibody geometric mean titer (GMT) on Day 56 between the treatment groups (CV1, CV2, A, B, C, D, M1, M2).

GMTs and GMT ratios will be estimated with including the factor vaccination group. GMTs for the MV-CHIK groups will be compared pairwise.

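### Protocol 13.4 says the planned analysis has more power than the t-tests behind its 80% figures; with Tukey-Kramer adjustment it has less, about 41–48% for the dose contrast at the protocol's SD

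*Protocol*

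**What the plan says.** Protocol 13.4 gives two power statements.

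- Between doses: a "GMT of 45.7 vs. 22.4" with 60 per group, "SD 0.6 for both groups) with a statistical power of 80" per cent ("two-sided alpha=5%, equal-variance t-test").
- Vaccine against control: a GMT of 15.4 vs 7.3, log10 SD 0.6 vs 0.26, 60 vs 10 subjects, also 80% ("two-sided alpha=5%, unequal-variance t-test").

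It then says that "the statistical methodology applied in the current study has a higher statistical power than pairwise t-tests" and concludes that the size seems adequate.

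The planned analysis is described elsewhere. Protocol 13.1 specifies an ANOVA on log10 titres with p-values for "pairwise comparisons adjusted for multiple comparisons according to Tukey-Kramer; groups A vs. B, C vs. D, M1 vs. M2". SAP 2.7 says "Pairwise comparisons for multiple comparisons will be adjusted according to Tukey-Kramer". SAP 2.7.1 compares Day 56 GMTs "between the treatment groups (CV1, CV2, A, B, C, D, M1, M2"), an eight-level factor, and adds that the MV-CHIK groups are compared pairwise.

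**The concern.** A one-way ANOVA can gain a little over a pairwise t-test, because it estimates the error from all groups. Tukey-Kramer works the other way: it raises the critical value so that the error rate holds over every pair in the family. With eight groups there are 8 × 7 / 2 = 28 pairs. The sentence in 13.4 credits the planned method with the small gain and ignores the much larger loss.

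The comparisons do not line up either. The dose contrast powered in 13.4 is not among the three pairs in Protocol 13.1, none of which sets low against high dose. It does fall within SAP 2.7.1, which takes all MV-CHIK pairs. The 60 vs 10 control comparison does not exist under SAP 2.3, which groups controls by schedule into CV1 and CV2.

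Identifying a dose and schedule for Phase 3 is a secondary objective. Someone reading 13.4 would take power for a two-fold dose difference to be at least 80% and would read the adjusted p-values in that light.

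**Working it through.** **Inputs.** GMTs, SDs, group sizes, alpha and tests are from Protocol 13.4. The eight factor levels are from SAP 2.7.1. N = 320 is from Protocol Table 1, so error df = 320 − 8 = 312. Each of CV1 and CV2 has 10 + 10 = 20 controls (Table 1 counts with the SAP 2.3 grouping). SD 0.26 for M2 at Day 56 is an assumption: M2 has had no MV-CHIK by then.

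**Step 1: reproduce the 80% figures (noncentral t).**
- Dose: Δ = log10(45.7/22.4) = 0.3097; SE = 0.6 × √(2/60) = 0.1095; Δ/SE = 2.83; df 118; critical value 1.98. Power **80.1%**.
- Vaccine vs control: Δ = log10(15.4/7.3) = 0.3242; SE = √(0.6²/60 + 0.26²/10) = √(0.00600 + 0.00676) = 0.1130; Δ/SE = 2.87; Satterthwaite df 28.6. Power **79.2%**.

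Both match, with no multiplicity adjustment.

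**Step 2: what the ANOVA gains.** For the dose contrast with SD 0.6 throughout, moving from 118 to 312 df lowers the critical value from 1.980 to 1.968. Power goes from 80.1% to **80.5%**.

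**Step 3: what the adjustment costs.** The Tukey critical value is q(0.95; k, 312)/√2. For k = 8 it is 4.316/1.414 = 3.052. Same Δ/SE of 2.83:

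| Family | Critical value | Power, dose contrast |
|---|---|---|
| Tukey, all 8 groups | 3.052 | 41% |
| Tukey, 6 MV-CHIK groups | 2.868 | 48% |
| Tukey, A–D only | 2.583 | 60% |
| Bonferroni, 3 pairs | 2.407 | 66% |

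The last row applies the protocol's family size to a contrast of this magnitude between two groups of 60. Under the eight-group family, 80% power would need a 2.67-fold difference instead of 45.7/22.4 = 2.04-fold, or about 114 per dose group.

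**Step 4: sensitivity to the SDs.** Low-titre groups with smaller SD shrink the pooled variance.
- CV1 and CV2 at 0.26: (38 × 0.0676 + 274 × 0.36)/312 = 0.3244, pooled SD 0.570.
- M2 at 0.26 as well: (57 × 0.0676 + 255 × 0.36)/312 = 0.3066, pooled SD 0.554.

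Power is approximately P(Z > [c × s × √(2/60) − Δ]/0.1095), where c is the critical value and s the pooled SD. Simulation gives 47% and 51% for eight groups, and 54% and 57% for six. Bonferroni for three pairs gives 71% and 73%. No adjusted reading examined reaches 80%. Unadjusted, the pooled test would show 83–84% here, but only because its error term is too small for groups with true SD 0.6.

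**Step 5: vaccine vs control, if placed in the eight-group pooled Tukey family (60 vs 20).** The rejection threshold is 3.052 × s × √(1/60 + 1/20) = 3.052 × s × 0.2582. The true SE is √(0.00600 + 0.00338) = 0.0969.
- s = 0.570 (CV1, CV2 at 0.26): power 10%.
- s = 0.554 (M2 also at 0.26): 13%.
- SD 0.6 in every group: 17%.

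Two effects combine. An unadjusted unequal-variance test of 60 vs 20 has 91%. Pooling the variance alone, with control SD 0.26, gives 64–67%. The Tukey critical value alone, with an unequal-variance SE, gives 62%.

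**The case against.** The strongest reply is that the size was never derived from power. Protocol 13.3 and SAP 1.4 rest it on feasibility and common practice, 13.4 says no formal calculation was made, and the SAP does not repeat the power claim. GMT ratios with 95% confidence intervals are planned, and no decision rule ties the Phase 3 dose to a significant p-value. All of this stands. It limits the consequence but does not make the sentence true, and 13.4 does infer adequacy from it.

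It is also fair to say that 41% is one reading. SAP 2.7.1 has eight factor levels but names pairwise comparison only for the MV-CHIK groups, which supports 48%. Hence the range.

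Three stronger readings are tempting, and the documents do not support them.

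- A reader might infer that vaccine-versus-control power is about 13%. That needs 20 merged controls, SD 0.26 for M2 as well as for the controls, pooled variance together with Tukey, and membership of the Tukey family. Neither document names these contrasts as Tukey-adjusted for the primary endpoint. The figure also assumes different SDs from the 41%; with the same SDs the dose contrast is about 51%.
- A reader might infer that the 320 subjects and the Phase 3 dose depend on this paragraph, or that a non-significant result will be taken as equivalence. The documents say the first is not so for the sample size and say nothing of the second.
- A reader might infer that Tukey-Kramer must be replaced. The error is in the power claim; the choice of adjustment is defensible.

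**Conclusion.** The sentence in Protocol 13.4 is wrong for the planned analysis under every adjusted reading examined, and nothing elsewhere in either document corrects it. For a 2.04-fold dose difference, power is about 41–48% with SD 0.6 in all groups, or about 47–57% if the low-titre groups have SD 0.26. The spread reflects whether eight or six groups form the Tukey family.

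For vaccine against control, the firm conclusion is that the powered comparison (60 vs 10, unequal variances) differs from the one the SAP grouping allows (60 vs 20). A power of roughly 10–17% holds only if those contrasts are tested in the pooled eight-group Tukey family, which is not settled.

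The two documents also define the comparison family differently, although SAP 2.17 states that no change from the protocol's planned analysis is intended. The arithmetic of the 80% figures is sound; the fault is attaching them to a different test.

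**What to change.** 1. In Protocol 13.4, delete the statement that the planned method has higher power. Say that the two 80% figures are for single, unadjusted two-sample t-tests.
2. Restate power for the adjusted analysis with its assumptions. For the dose contrast: about 41% (eight-group family) or 48% (six-group family) at SD 0.6, and 47–57% with SD 0.26 in the low-titre groups. For the control contrast, use the 20 controls per schedule that the analysis will have.
3. Make the Tukey family identical in Protocol 13.1 and SAP 2.7.1. List the pairs, say whether low versus high dose is among them, and say whether control contrasts are in or out.

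The cost is wording and a less favourable stated power, with no extra subjects. SAP Final 3.0 is dated 09-May-2018, after the preliminary analysis scheduled for August 2017. Any change to the family should therefore be recorded with its date and the state of knowledge at that time.

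A smaller prespecified set is open to the sponsor but is not needed to cure the error. For example, four dose and schedule contrasts (A–C, B–D, A–B, C–D) with Bonferroni would give about 62% at SD 0.6 (critical value 2.512).

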### 13.5 Analysis Populations

#### 13.5.1 Safety Population

All safety analyses for TEAEs will be based on the safety population, defined as subjects who entered into the study and received at least one vaccination. All analysis based on the Safety Population will be carried out using the actual treatment received. The denominators for reactogenicity rates are determined separately as discussed in section 0 (Safety Analysis).

### **13.5.2 Modified Intent-to-Treat (mITT) Population**

The exploratory immunogenicity analyses will be based on the modified ITT population. The modified intent-to-treat (mITT) analysis population is defined to include all subjects randomized who receive at least one vaccination.

### **13.5.3 Per-Protocol (PP) Population**

As a primary analysis, immunogenicity will be assessed on the per-protocol (PP) population. The PP population includes subjects who have received at least one vaccination. Subjects with protocol deviations that could have an impact on immune response will be excluded from the PP Population. Examples that may lead to exclusion from the PP population are provided here (further criteria may be defined in the SAP):

- Immunosuppressive drugs: Use of corticosteroids (excluding topical preparations) or immunosuppressive drugs within 30 days prior to vaccination, or anticipated use during the trial.
- Subjects with any confirmed immunosuppressive or immunodeficient condition, including human immunodeficiency virus (HIV), hepatitis A, B or C infection or a family history of congenital or hereditary immunodeficiency
- Subjects who received the wrong or no study medication

These criteria for potential protocol violation have been identified at the time of planning the study. However, during the course of the trial unforeseen events may occur or new scientific knowledge may become available, therefore final decisions on whether any protocol violation could impact immune response and thus lead to exclusion from the PP population will be made by the sponsor on a case by case basis in a blinded manner (and prior to study unblinding). Sample testing issues may also lead to exclusion from the PP population for particular time points.

## **14 ADVERSE EVENTS (AEs)**

### **14.1 Definition**

#### **14.1.1 Adverse Event (AE)**

An AE is any undesirable medical event occurring to a subject in a clinical trial, whether or not considered related to the trial product(s). This includes events not seen at baseline or worsened if present at baseline. The following should not be recorded as AEs, if recorded at screening (on Screening Form or eCRF):

- Pre-planned procedure, unless the condition for which the procedure was planned, has worsened since baseline.
- Pre-existing conditions found as a result of screening procedures.

#### **14.1.2 Clinical Laboratory Adverse Event**

A clinical laboratory AE is any clinical laboratory abnormality that suggests a disease and/or organ toxicity and is of a severity, which requires active management (i.e. changes of dose, discontinuation of drug, more frequent follow-up or diagnostic investigation).

#### **14.1.3 Serious Adverse Event (SAE)**

An SAE is any adverse experience that results in any of the following outcomes:

- death
- a life-threatening experience
- in-patient hospitalization or prolongation of existing hospitalization
- a persistent or significant disability/incapacity
- a congenital anomaly/birth defect.

Important medical events that may not result in death, are life-threatening\*, or require hospitalization will be considered a serious adverse event when they may jeopardize the health of the subject or patient and may require medical or surgical intervention to prevent one of the outcomes listed in this definition.

\* The term life threatening in the definition of serious adverse event refers to an event in which the subject was at risk of death at the time of the event. It does not refer to an event, which hypothetically might have caused death if it was more severe.

#### **14.1.4 Non-Serious Adverse Event**

A non-serious adverse event is any AE, which does not fulfill the definition of an SAE.

#### **14.1.5 Medically-attended events (MAEs)**

Medically-attended events (MAEs) refer to non-serious and serious events leading to an otherwise unscheduled visit to or from medical personnel for any reason, including emergency room visits.

### **14.2 Severity Assessment Definitions**

Mild: Transient symptoms, no interference with the subject's daily activities

Moderate: Marked symptoms, moderate interference with the subject's daily activities

Severe: Considerable interference with the subject's daily activities, unacceptable.

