**Table 9 Grading of systemic reactions**

Systemic Reaction (General)	Mild (grade 1)	Moderate (grade 2)	Severe (grade 3)	Potentially life threatening (grade 4)
Nausea/vomiting	No interference with activity or 1-2 episodes/ 24 hours	Some interference with activity or >2 episodes/ 24 hours	Prevents daily activity, requires outpatient IV hydration	Emergency room (ER) visit or hospitalization for hypotensive shock
Diarrhea	2-3 loose stools or < 400 gms/ 24hours	4-5 stools or < 400-800 gms/ 24hours	6 or more watery stools or >800 gms/ 24 hours or requires outpatient IV hydration	ER visit or hospitalization
Headache	No interference with activity	Repeated use of non-narcotic pain reliever >24 hours or some interference with activity	Significant; any use of narcotic pain reliever or prevents daily activity	ER visit or hospitalization
Fatigue	No interference with activity	Some interference with activity	Significant; prevents daily activity	ER visit or hospitalization
Myalgia	No interference with activity	Some interference with activity	Significant; prevents daily activity	ER visit or hospitalization
Illness or clinical AE (as defined according to applicable regulations)	No interference with activity	Some interference with activity not requiring medical intervention	Prevents daily activity and requires medical intervention	ER visit or hospitalization
Fever (°C) (°F)	38.0-38.4 100.4-101.1	38.5-38.9 101.2-102.0	39.0-40.0 102.1-104.0	>40.0 >104.0

In addition, any signs and symptoms of arthralgia will be carefully assessed. Importantly, subjects will be asked if they experience any signs of limb pain or joint pain, to distinguish symptoms of arthralgia from flu like symptoms including limb pain.

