### **Individual subjects**

The following subjects will be discontinued from further vaccination:

- a. Subjects who develop a severe or life-threatening (grade 3 or 4) suspected adverse reaction (SAR) or laboratory abnormality.
- b. Subjects who develop a grade 3 solicited systemic adverse event that occurs without alternative etiology in the 7 days following the study vaccination.
- c. Subjects who develop a medical condition for which continued participation, in the opinion of the site principal investigator or appropriate sub-investigator, would pose a risk to the subject or would be likely to confound interpretation of the results.
- d. Pregnant subjects.

In case a subject has to discontinue the clinical study prematurely for any reason, he or she should be asked to perform an early termination visit. Additionally, women of childbearing potential will be followed up by a phone call, 3 months after the last vaccination to ensure no pregnancy occurred within this period as confirmed by a urine pregnancy test provided by the investigator.

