### **Treatment group stopping rules**

If four or more subjects in a treatment group experience a treatment related grade 3 suspected adverse reaction (SAR) or laboratory abnormality, or one or more subjects in a treatment group experience a treatment related grade 4 SAR or laboratory abnormality, the study will be suspended pending an unblinded safety review of those subjects by the DSMB. This safety review might lead to the recommendation to discontinue a treatment group.

In case a treatment group has to discontinue the clinical study prematurely for any reason, the concerned subjects should be asked to perform an early termination visit. Additionally, women of childbearing potential will be followed up by a phone call, 3 months after the last vaccination to ensure no pregnancy occurred within this period as confirmed by a urine pregnancy test provided by the investigator.

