2.11 Handling Missing Data

In general, missing data will not be imputed. However, for adverse events missing assessments for severity, causality and seriousness will be imputed with the worst case (severity=severe, causality=definitely and seriousness=yes).

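### Unsolicited adverse events have no named severity scale, and under Protocol 14.2 a related one cannot reach the one-subject grade 4 stopping trigger

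*Protocol*

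**What the plan says.** Two places in the protocol could grade an unsolicited event.

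- **Section 14.2**, in the AE chapter, has three levels. The middle one is "Moderate: Marked symptoms, moderate interference with the subject's daily activities" and the top one is "Severe: Considerable interference with the subject's daily activities, unacceptable". There is no fourth level.
- **Table 9**, in 11.2.4, has a row labelled "Illness or clinical AE (as defined according to applicable regulations" with grades 1 to 4. Grade 2 is "Some interference with activity not requiring medical intervention", grade 3 is "Prevents daily activity and requires medical intervention", and grade 4 is an emergency-room visit or hospital admission.

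Section 13.2 tabulates unsolicited events by grade without naming a scale.

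The rules that use the grades are in 11.3. The individual rule stops further vaccination for "Subjects who develop a severe or life-threatening (grade 3 or 4) suspected adverse reaction (SAR) or laboratory abnormality", which pairs severe with grade 3 and life-threatening with grade 4. The group rule suspends the study for review by the data safety monitoring board (DSMB) when four or more subjects in a group have a related grade 3 reaction, or when "one or more subjects in a treatment group experience a treatment related grade 4 SAR or laboratory abnormality". Under 14.3 a suspected adverse reaction (SAR) is any event rated possibly, probably or definitely related, so unsolicited events count.

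SAP 2.11 says that missing AE severity, causality and seriousness "will be imputed with the worst case (severity=severe, causality=definitely and seriousness=yes"). SAP 8.3 and Tables 4.3 and 4.5 count severe unsolicited events without defining severe.

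**The concern.** The group rule turns on the difference between grade 3 and grade 4, because the threshold drops from four subjects to one. A scale that ends at severe cannot supply that difference. If investigators grade unsolicited events by 14.2, the one-subject trigger does not exist for them. If they use Table 9, it does. No text settles which applies, so the same event can count differently at different sites (the protocol lists six).

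The two scales also draw the lower boundaries differently, and the Table 9 row is not exhaustive. That bears on what counts as grade 3 in the individual and group rules, and on the severe-event tables in the SAP.

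**Working it through.** **Step 1: put the scales side by side.** Take three related unsolicited events.

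| Event | Under 14.2 | Under the Table 9 row | Effect in 11.3 |
|---|---|---|---|
| (a) Leads to an emergency-room visit | At most severe, i.e. grade 3 by the pairing in the individual rule | Grade 4 | One of four subjects needed, or suspends alone |
| (b) Prevents daily activity, no medical intervention | Severe | No grade: grade 3 also requires intervention, and grade 2 covers only some interference | Counts as grade 3, or has no defined status |
| (c) Some interference, and intervention was needed | Moderate, if some is read as moderate interference | No grade: grade 2 excludes intervention, grade 3 requires that activity is prevented | Does not count, or has no defined status |

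Case (a) arises from the missing fourth level. Cases (b) and (c) arise from gaps within the Table 9 row, and would remain if that row alone were adopted.

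**Step 2: find what catches case (a) by another route.** The entire-study rule in 11.3 stops everything for one SAR that is both serious and unexpected, and severity grade plays no part. A hospital admission is serious by 14.1.3. Section 11.1 also has the DSMB review every serious AE within a week of its report. What escapes the automatic stop is a related emergency-room visit that meets no seriousness criterion (14.1.5 recognises that medically attended events, including such visits, can be non-serious), or a hospitalization already expected at that severity.

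**Step 3: illustrate the size.** The plan gives no operating characteristics for the stopping rule, so there is no stated figure to reproduce. Inputs from Table 1 and Protocol 6.3: n = 60 + 10 = 70 in each of groups A to D, and n = 20 in each of M1 and M2. Assumptions: each subject independently has probability p = 1% of a residual event from Step 2, and there are no other grade 3 events.

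- Threshold 1 (event graded 4): P(X ≥ 1) = 1 − (1 − p)^n
- Threshold 4 (same event capped at severe): P(X ≥ 4) = 1 − Σ over k = 0 to 3 of C(n,k) p^k (1 − p)^(n−k)

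For n = 70:
- 1 − 0.99^70 = 1 − 0.4948 = 0.5052
- 1 − (0.4948 + 0.3499 + 0.1219 + 0.0279) = 0.005

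For n = 20:
- 1 − 0.99^20 = 1 − 0.8179 = 0.1821
- The leading term of P(X ≥ 4) is 4845 × 0.01^4 × 0.99^16 ≈ 0.00004, so the probability is below 0.01%

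Over a range of assumed rates:

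| Assumed p | n = 70, threshold 1 | n = 70, threshold 4 | n = 20, threshold 1 | n = 20, threshold 4 |
|---|---|---|---|---|
| 0.5% | 29.6% | 0.04% | 9.5% | <0.01% |
| 1% | 50.5% | 0.5% | 18.2% | <0.01% |
| 2% | 75.7% | 5.2% | 33.2% | 0.06% |
| 5% | 97.2% | 46.6% | 64.2% | 1.6% |

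If the 10 control recipients are taken out of a group, as SAP 2.3 does for analysis, n = 60 gives 45.3% against 0.3% at p = 1%.

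The threshold-4 figures are lower bounds, because other related grade 3 reactions or laboratory abnormalities also count towards the four. For example, if all such events together had a 5% rate, the four-subject rule alone would fire with probability 46.6% in a group of 70.

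**The case against.** The best defence is that there are not two competing scales. Table 9 is headed as grading systemic reactions, sits in the tolerability section and follows a list of diary symptoms, whereas 14.2 sits in the AE chapter. The SAP can be read the same way: grades 1 to 4 for diary symptoms (2.13), and severe as the top for AEs (2.11). This has force, and applying the Table 9 row to unsolicited events is an inference. But the row is not one of the diary symptoms named there, and no other graded row fits a general clinical event. If the defence is accepted in full, unsolicited events have only 14.2, and the one-subject trigger has no level for them. The defect then changes form but remains.

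The second defence is the set of backstops in Step 2, together with the DSMB's role in judging unblinded whether a rule is met. These narrow the gap considerably. They do not close it, because site grades are still the input to the counts.

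Four stronger readings are tempting and are not supported:

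- **A related hospitalization would merely be one of four.** If it is also unexpected, it stops the entire study whatever its grade.
- **The missing fourth level changes individual discontinuation.** It does not, because that rule acts on grade 3 or grade 4 alike. Only cases (b) and (c) bear on it.
- **SAP 2.11 is a further contradiction.** It is consistent with 14.2.
- **Phase 1 gives the event rate.** Its 2 of 42 subjects (4.8%) with serious unsolicited events are not restricted to related ones.

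The eCRF and the DSMB charter, which might settle the matter, are not available, so it cannot be said that sites actually used different scales.

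**Conclusion.** The concern holds in a limited form. The protocol sets different thresholds for grades 3 and 4, but does not name the scale that assigns those grades to unsolicited events, and the scale in its AE chapter cannot produce a grade 4. Separately, the Table 9 row leaves two kinds of event ungraded. Neither conclusion depends on an assumed rate.

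The practical exposure is mainly related emergency-room events that meet no seriousness criterion, and hospitalizations already expected. For those, at an assumed 1% rate and with no other grade 3 events, the choice of scale moves the chance that the group rule fires from 0.5% to 50.5% in a group of 70, and from below 0.01% to 18.2% in a group of 20. With background grade 3 events the contrast would be smaller.

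**What to change.** Reconcile Protocol 14.2, the general-AE row of Table 9, the individual and group rules in 11.3, and SAP 2.11 and 8.3, so that:

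1. one named scale, with levels that are exhaustive and do not overlap, is recorded on the eCRF for unsolicited events;
2. the protocol states how its levels map to grades 3 and 4;
3. the protocol and SAP state that this scale feeds both the 11.3 counts and SAP Tables 4.3 and 4.5; and
4. the worst-case value imputed under SAP 2.11 is expressed on the same scale.

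Which clinical definition applies is for the sponsor and the DSMB to decide.

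The cost is protocol and SAP wording, an eCRF completion instruction, and some regrading of events already recorded, preferably blind to allocation. No extra visits or subjects are needed.
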